### **3. Revision History**

Statistical Analysis Plan (SAP) Version 1 was approved prior to the first visit when a subject receives study drug or any other protocol intervention.

## 4. Study Objectives

### 4.1. Primary Objective

The primary objective of this study is to assess the safety and tolerability of LY3434172, thereby identifying a recommended Phase 2 Dose (RP2D) to be administered to patients with advanced solid tumors.

### 4.2. Secondary Objectives

- to assess the pharmacokinetics (PK) of LY3434172 in patients with solid tumors
- to assess the preliminary antitumor activity of LY3434172

### 4.3. Tertiary/Exploratory Objectives

- to characterize tumor tissue and blood biomarkers relevant to LY3434172, including but not limited to immune cells/immune functioning, mechanism of action of study drugs, cancer-related pathways, and disease state
- to explore the association among biomarkers, doses, concentrations, and clinical outcomes
- to assess the immunogenicity of LY3434172 in patients with advanced solid tumors
- to assess progression-free survival (PFS) and overall survival (OS) of patients receiving LY3434172 administered as monotherapy

## 5. Study Design

### 5.1. Summary of Study Design

CCI

CCI

CCI

The dose escalation will employ a modified toxicity probability interval 2 (mTPI2) method along with PK/pharmacodynamic analysis to identify an RP2D. The RP2D will be determined based on the number of observed dose-limiting toxicities (DLTs) and PK/pharmacodynamic data. The RP2D may be below the maximum tolerated dose (MTD), which may not necessarily be reached during the dose escalations.

The DLT observation will include the observation period (Cycle 1, 42 days) for Cohort A1 (Cycle 1, 28 days); for Cohorts A2 to A5 (A2 to A6 if Cohort A6 is opened; Cycle 1 and 2, 42 days); and for Cohorts A7 and A8. Once the DLT period is completed for respective Cohorts A1 to A5/6, up to approximately 12 to 15 additional patients may be added to 2 dose levels selected from Cohorts A4 and A5/6 ([Figure JZEA.5.1](#)).

## 6. A Priori Statistical Methods

### 6.1. Sample Size Determination

The sample size determination is described in Section 10.1 of Protocol JZEA.

### 6.2. General Considerations

Statistical analysis of this study will be the responsibility of Eli Lilly and Company (Lilly) or its designee.

Sponsor standard tables, figures, and listings (TFLs) and supporting programs and software (eg, SAS®) will be utilized for all analyses where a suitable standard exists. Data derivations in this SAP are defined based upon current sponsor reporting standards at the time of writing, and may be updated at the time of analysis in order to maintain accordance with the most current sponsor standards at that time.

Unless otherwise noted, **summaries of continuous variables** will include a mean, median, standard deviation, minimum, and maximum. When appropriate, lower and upper quartiles will also be presented.

Unless otherwise noted, **summaries of categorical variables** will include the frequency and percentage (relative to the population being analyzed) of each category.

Unless otherwise stated, data will be summarized by dose escalation cohorts that will indicate the assigned treatment regimen and dose schedule for LY3434172.

In addition, safety data may be summarized by the same treatment regimen and dose schedule, and efficacy data may be summarized by the same indication and treatment regimen.

Additional exploratory analyses of the data will be conducted as deemed appropriate.

#### 6.2.1. Populations

The following population will be defined for this study:

**Entered population:** will include all patients who sign the informed consent document.

**Enrolled/safety population:** will include all patients who received any quantity of study treatment (LY3434172), regardless of their eligibility for the study. The safety and efficacy evaluation will be performed based on the first dose of study treatment a patient actually received. This population will be used for all dosing/exposure, safety, and efficacy analyses.

**Dose-limiting toxicity–evaluable population:** will include all patients from the study who have completed the DLT observation period (Cycle 1) or discontinued treatment before the end of the DLT observation period but with a documented DLT assessment. Exposure and safety summaries may be repeated for this population.

**Pharmacokinetic population:** will include all enrolled patients from whom a valid assay result (according to laboratory guidelines) has been obtained.

**Biomarker population:** will include the subset of enrolled patients from whom a valid assay result has been obtained. No imputation will be performed for missing data due to the limitation of small sample size.

### 6.2.2. Definitions and Conventions

The following definitions and data handling conventions will be used in the analysis.

**Table JZEA.6.1. Definitions and Data Handling Conventions**

Term	Definition or Rule
Relative Study Day	If assessment is on or after date of first dose, then (date of assessment) – (date of first study drug dose) +1
	If assessment precedes first dose of drug, then (date of assessment) – (date of first study drug dose)
	There is no Study Day 0. Study Day 1 is the date of first dose and Study Day -1 is the day before the first dose.
Cycle Day	If assessment is on or after date of first dose in cycle, then (date of assessment) – (date of first study drug dose in cycle) +1
	There is no Cycle Day 0. Cycle Day 1 is the date of first dose in that cycle.
Baseline	For change from baseline analyses, baseline value is defined as the last reported measure on or before the first dose date (prior to the dose administration), unless otherwise specified.
Age (years)	Age is based on date of birth and informed consent date. If only a year and month are provided in the date of birth, set day to 15. If only a year is provided, set day to 1 and month to 7 (July).
Duration	Duration (days): (End Date – Start Date + 1)
	Duration (weeks): (End Date – Start Date + 1)/7
	Duration (months): (End Date – Start Date + 1)/30.4375 (Days in months = (1/12)*average number of days in a year)
	Duration (years): (End Date – Start Date + 1)/365.25 (Average days in a year = 365.25, reflecting the Julian Year of 3 years with 365 days each and 1 leap year of 366 days)
Time-to-Event	The event or censoring time (days) is calculated as: Date of event/censoring – Date of first dose of study drug + 1

### 6.3. Adjustments for Covariates

Given the small sample size for each tumor type and treatment, no formal analysis investigating the impact of covariates is planned. If data warrant, exploratory analyses may incorporate patient disease characteristics in evaluation of efficacy parameters.

### 6.4. Handling of Dropouts or Missing Data

Missing data, except for dates, will not be imputed. They will be kept as missing in the data analyses, except for dates when used in calculations of relative study day, for which sponsor reporting standards will be utilized for imputation rules, defined as: Missing start days will be replaced with 1 and missing day/month with 01 JAN. Missing end days will be replaced with the last day of the month, and missing day/month with 31 DEC. The imputation rule may be updated at the time of study reporting if necessary to maintain accordance with most recent sponsor standards. Partial dates should be reported in all listings and not the imputed date.

For time-to-event endpoints, the method for handling missing data will be censoring. Additional sensitivity analyses may be conducted applying different censoring rules if data warrant and will follow sponsor-defined standards.

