**Table JZEA.6. Objectives and Endpoints**

Objectives	Endpoints
Primary	
To assess the safety and tolerability of LY3434172, thereby identifying a RP2D of LY3434172, administered to patients with advanced solid tumors.	
 
• DLTs
 
• Safety (including but not limited to): TEAEs, DLT-equivalent toxicities, SAEs, deaths, and clinical laboratory abnormalities per CTCAE (Version 5.0)
 

Secondary	
To assess the PK in patients with solid tumors of LY3434172.	
 
• AUC, <math>C_{\min}</math> and approximate <math>C_{\max}</math> of LY3434172
 

To assess preliminary antitumor activity a of LY3434172	
 
• ORR
 
• DOR
 
• TTR
 
• DCR
 

Tertiary/Exploratory	
To characterize tumor tissue and blood biomarkers relevant to LY3434172, including but not limited to immune cells/immune functioning, mechanism of action of study drugs, cancer-related pathways, and disease state	
 
• Results of biomarker analyses
 
• Clinical outcomes
 

To explore the association between biomarkers and dose, concentrations and clinical outcomes	
 
• Results of biomarker analyses
 
• Clinical outcomes
 

To assess the IG of LY3434172 in patients with advanced solid tumors.	
 
• Relationship between TE ADA and safety
 
• Relationship between TE ADA and LY3434172 pharmacokinetics.
 

To assess PFS and OS of patients receiving LY3434172.	
 
• PFS
 
• OS
 

Abbreviations:  $C_{\max}$  = maximum serum/plasma concentration;  $C_{\min}$  = minimum serum/plasma concentration; CTCAE = Common Terminology Criteria in Adverse Events; DCR = disease control rate; DLT = dose-limiting toxicity; DOR = duration of response; IG = immunogenicity; ORR = objective response rate; OS = overall survival; PFS = progression-free survival; RECIST = Response Evaluation Criteria in Solid Tumors; RP2D = recommended Phase 2 dose; SAE = serious adverse event; TEAE = treatment-emergent adverse event; TE ADA = Treatment-emergent anti-drug antibodies; TTR = time-to-response.

a Response assessment using RECIST 1.1 and RECIST 1.1 with confirmatory scan for disease progression.

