screen	The act of determining if an individual meets minimum requirements to become part of a pool of potential candidates for participation in a clinical study.
Screen failure	A patient who does not meet one or more criteria required for participation in a study
SEC	staphylococcal enterotoxin B
sPD-L1	soluble programmed death ligand 1
SOC	system organ class
SUSAR	suspected unexpected serious adverse reactions
TBL	total bilirubin
TE	target engagement
TEAE	Treatment-emergent adverse event: an untoward medical occurrence that emerges during a defined treatment period, having been absent pretreatment, or worsens relative to the pretreatment state, and does not necessarily have to have a causal relationship with this treatment.
TMDD	Target Mediated Drug Disposition
TTR	Time-to-response

**Vd** volume of distribution

**WOCBP** Women of childbearing potential; females who have attained menarche and are not menopausal or surgically sterile.

---

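### Partial start dates are imputed to day 1 or 1 January with no floor at first dose, so early on-treatment AEs can get negative study days and, depending on programming, miss the TEAE tables

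*SAP*

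**What the plan says.** SAP 6.4 leaves missing data missing, "except for dates when used in calculations of relative study day". For those dates, "Missing start days will be replaced with 1 and missing day/month with 01 JAN". Nothing in the rule refers to the date of first dose. The section adds that "The imputation rule may be updated at the time of study reporting if necessary to maintain accordance with most recent sponsor standards", and that listings show the partial date rather than the imputed one.

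SAP Table JZEA.6.1 defines relative study day. On or after first dose it is the date minus the first-dose date, plus 1. The other branch begins "If assessment precedes first dose of drug" and omits the plus 1, so the result is negative.

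Protocol Table JZEA.6 puts TEAEs in the primary safety endpoint: "TEAEs, DLT-equivalent toxicities, SAEs, deaths, and clinical laboratory abnormalities per CTCAE (Version 5.0"). Protocol Appendix 1 defines a TEAE as "an untoward medical occurrence that emerges during a defined treatment period, having been absent pretreatment, or worsens relative to the pretreatment state". SAP 6.12.3 plans the TEAE summaries but gives no derivation from dates. SAP 6.19 admits a non-serious AE to the registry table only if it is a TEAE. Neither document gives any other rule for a partial AE start date.

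**The concern.** The first of the month, or of the year, is never later than the true onset. The rule can therefore move an on-treatment onset to before first dose, but it cannot move a pre-dose onset to after it. The onsets at risk are the early ones.

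AEs are recorded from consent (Protocol 9.2.1), so pre-dose and on-treatment events sit in one dataset and something must separate them. The study day or the imputed start date is an obvious candidate. If a programmer uses either, an early on-treatment event with a partial date is classed as pre-treatment and leaves the TEAE tables. If neither is used, a partial-date AE has no stated rule for its TEAE status. Either way, a component of the primary endpoint is not fully specified.

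**Working it through.** The plan gives no figure to reproduce and tests no hypothesis. The check applies its two rules to calendar dates.

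**Inputs from the SAP.** The imputation in 6.4 and the study-day formula in Table JZEA.6.1.

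**Assumptions.** First dose is equally likely on each of the 365 days of 2019. True onset is uniform over the first W days from first dose. All shares are conditional on the date being partial.

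**Single cases**

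| First dose | True onset | True study day | Day missing | Day and month missing |
|---|---|---|---|---|
| 17 Jun | 20 Jun | 4 | -16 | -167 |
| 1 Jun | 20 Jun | 20 | 1 | -151 |
| 17 Jun | 5 Jul | 19 | 15 | -167 |

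For the first row, 1 Jun minus 17 Jun is -16, and 1 Jan minus 17 Jun is -167. The second row shows that dosing on the 1st gives no negative day when only the day is missing. The third shows that a known later month keeps the study day positive.

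**Shares for W = 28.** There are 365 × 28 = 10,220 pairs of first dose and onset.

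- *Day missing.* A pair escapes if first dose is on the 1st (28 pairs per month) or if onset falls in a later month (27 + 26 + … + 1 = 378 pairs per month). Escaping pairs: 12 × (28 + 378) = 4,872. Share made negative: 1 − 4,872/10,220 = 52.3%.
- *Day and month missing.* A pair escapes if first dose is on 1 January (28) or if onset falls in the next year (378). Escaping pairs: 406. Share made negative: 1 − 406/10,220 = 96.0%.

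**Other windows, by enumeration**

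| W (days) | Day missing | Day and month missing |
|---|---|---|
| 7 | 86.8% | 98.9% |
| 14 | 75.3% | 97.9% |
| 28 | 52.3% | 96.0% |
| 42 | 35.0% | 94.1% |
| 90 | 16.4% | 87.5% |

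**With a floor at first dose.** For the missing-day case, taking the later of the current-rule date and the first-dose date when the months match brings the share to 0% in every window. The 20 June onset becomes study day 1. The same follows when day and month are missing: a matching year is floored at first dose, and 1 January of a later year is already after first dose.

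**Cost of the floor.** Spread true onsets evenly over the 28 days before first dose. With first dose on day d of its month, for d up to 28, 28 − (d − 1) of these onsets fall in an earlier month; for later d, none do. Summed over a month this is 28 + 27 + … + 1 = 406, so 12 × 406 = 4,872 of 10,220 lie in an earlier month and 52.3% share the first-dose month. By the same count, 406 of 10,220 lie in the previous year and 96.0% share the first-dose year. Those with the corresponding date parts missing would move to study day 1 unless the end date excludes them.

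**The case against.** The strongest objection is that the link from study day to TEAE status is not in the documents. SAP 6.4 confines imputation to relative study day, Table JZEA.6.1 does not mention TEAEs, and Appendix 1 defines a TEAE by concept. That stands. A reader might infer that these events will be lost from the TEAE counts. The documents support only that they can be, if status is programmed from the imputed date or study day.

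A reader might also infer that dose escalation is at risk, because the misplaced events cluster in Cycle 1 and cohorts start at three patients. The documents do not support this. A DLT rests on the investigator's judgement of the event (Protocol 7.2.2.2), and escalation is decided in discussion between the investigators and the sponsor (Protocol 10.3.4). Imputed dates have no stated part in either.

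The percentages apply only to partial dates. These should be uncommon early on: Q2W patients have samples scheduled on Days 1, 2, 4, 8, 15, 16 and 22 (Protocol Appendix 4), and AEs are collected at every visit. An AE in that period with both day and month missing would be rarer still. This stands, and no unconditional effect can be given.

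Much safety reporting does not depend on TEAE status. All AEs are listed by patient, the overall row for at least one SAE is not limited to TEAEs (SAP 6.12.3), and registry SAEs count regardless (SAP 6.19). Treatment-emergent SAE summaries would be exposed.

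The allowance to update the rule at reporting does not answer the point. It commits the sponsor to no particular rule and leaves the choice open until after safety data have been seen in an open-label study.

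**Conclusion.** The point holds in limited form. As written, the rule gives a wrong study day, always in the same direction, to on-treatment AEs whose partial date matches the month or year of first dose, apart from dosing on the 1st or on 1 January. With uniform onset over 28 days, that is about 52% of AEs with the day missing and 96% with day and month missing. Over 90 days it is about 16% and 88%.

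If TEAE status is programmed from that date, the effect falls on the TEAE summaries and the registry table of other AEs. A patient-level count changes, for instance from 1/3 to 0/3, only when the patient has no other qualifying event. That is less likely for any TEAE than for Grade 3 or higher or a single preferred term. The absolute effect is unknown because the frequency of partial dates is not given, and it is probably small. A general claim that the drug will look safer, or that DLT counts or mTPI-2 decisions are biased, goes beyond the documents. The correction is still worth making, because it is cheap and concerns part of the primary endpoint.

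**What to change.** Add to SAP 6.4, for AE start dates:

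- If the day is missing and month and year equal those of first dose, or if day and month are missing and the year equals that of first dose, and the AE end date is not before first dose, impute the later of the current-rule date and the first-dose date.
- In all other cases apply the current rule, so that an AE with a known later month keeps that month.
- Determine TEAE status from this date.

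The match to the first-dose month or year matters. A looser rule that sent every compatible partial date to first dose would move an AE dated July to 17 June when dosing began on 17 June, against its known month.

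The cost is a short SAP addition and a small programming change. The downside is that pre-dose AEs with a missing day in the first-dose month, or with day and month missing in the first-dose year, would be counted as TEAEs unless the end date or another record shows pre-dose onset. That error is towards reporting harm, which is the safer direction in a first-in-human study.

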## **6.5. Multicenter Studies**

Given the small number of patients for each tumor type and treatment, patients across all sites will be grouped together for analysis purposes.

## **6.6. Multiple Comparisons/Multiplicity**

No formal hypothesis testing is planned for this study; thus, there will be no adjustments for multiplicity.

## **6.7. Patient Disposition**

Patient disposition will be summarized and listed for all patients entered into the study. It will include a summary of the number and percentage of patients entered into the study, enrolled in the study, and treated as well as number and percentage of patients completing the study, or discontinuing (overall and by reason for discontinuation of study drug). All patient discontinuation data collected on the case report form will be listed.

Important protocol deviations that potentially compromise the data integrity and patients' safety will be summarized for the safety population. These deviations will include those that can be identified programmatically and those that can only be identified by the clinical research associate during monitoring. Important protocol deviations are described in a separate document within the study Trial Master File.

## **6.8. Patient Characteristics**

Patient characteristics will be summarized and listed for the safety population. Details of the patient characteristics are described in the following sections. Other patient characteristics will be summarized as deemed appropriate.

### **6.8.1. Demographics**

Patient demographics will include sex, race, ethnicity, country, age, age group (<65 years; ≥65 years; <70 years; ≥70 years), height, weight, and body mass index.

### **6.8.2. Baseline Disease Characteristics**

Baseline disease characteristics will include Eastern Cooperative Oncology Group (ECOG) performance status (PS), initial pathological diagnosis, basis for initial diagnosis, disease stage, histopathological grade, tobacco usage (never, current, former), and alcohol use.

### **6.8.3. Prior Therapies**

Prior radiotherapy, surgery, and systemic therapy will be summarized. Prior radiotherapy will be categorized by reason for the regimen (neoadjuvant, adjuvant, neoadjuvant plus adjuvant, advanced/metastatic), and prior surgery will be categorized by intent (curative, palliative). Prior

systemic therapies will be categorized by setting (neoadjuvant, adjuvant, locally advanced, metastatic). Frequency of each specific therapy will be tabulated within each type of regimen and reason for regimen.

Patients who received any prior anti-programmed death 1 (PD-1) and/or anti-programmed death ligand 1 (PD-L1) therapies will be summarized and listed.

#### **6.8.4. Historical Illnesses**

Historical illnesses are events in the past that ended before the date on which the informed consent form was signed. Historical illnesses (coded according to the Medical Dictionary for Regulatory Activities [MedDRA]) will be listed for all enrolled patients.

#### **6.9. Treatment Compliance**

LY3434172 will be administered intravenously at the investigational sites only. As a result, patient compliance will be ensured. Any cases deemed as not compliant will be reported as protocol deviations.

#### **6.10. Concomitant Therapy**

Concomitant medications will be summarized and listed for the safety population.

For corticosteroids and/or immunosuppressives, the indication, administration route, individual dose, duration, dose adjustment, and reason for use will be summarized and listed.

#### **6.11. Postdiscontinuation Therapy**

The numbers and percentages of patients reporting postdiscontinuation therapies will be provided overall, by type of therapy (surgery, radiotherapy, or systemic therapy), and by drug name.

#### **6.12. Safety Analyses**

All patients who receive any quantity of LY3434172 will be evaluated for safety and toxicity. Details of the analyses are described in the following subsections.

##### **6.12.1. Extent of Exposure**

A summary of exposure will be provided for study drug, including cycle received, cumulative dose, and duration of therapy. Duration of therapy is defined as Discontinuation date – Date of first dose + 1.

A summary of dose intensity will be provided for study drug. Dose intensity expressed in mg/week will be calculated as the actual cumulative amount of drug taken divided by the duration of exposure in weeks. Duration of exposure in weeks is defined as (Date of last dose – Date of first dose + 14)/7 for every 2 weeks (Q2W) dose, and (Date of last dose – Date of first dose + 21)/7 for every 3 weeks (Q3W) dose.

Relative dose intensity will be calculated as:

$$100\% \times (\text{actual cumulative dose taken [mg]} / \text{planned cumulative dose [mg]})$$

Note that planned dose is the same as actual dose if there is no dose modification or cycle delay.

A summary of dose adjustments will be provided for study drug, including dose omissions, dose reductions, dose increases, dose delays, treatment interrupted, and the corresponding reasons for dose adjustments for each cohort.

